4.6 Sample Size and Power Calculation

Using historical Vaccine Confidence Index (VCI) data⁷⁰ and current vaccination rates⁷¹, a VCI threshold was determined that was significantly correlated with rates of vaccination ($p=0.0001$). Assuming the analytic approaches outlined in sections 4.7.2 and later, the sample size of 1,800

LTCWs (600 per arm) provides 80% power to detect an 8% difference in the rate of scores above this threshold between groups with a two-sided test at type I error rate of 0.05. The sample size is sufficient to retain 80% power to detect a 10% difference (assuming outcomes are randomly distributed across retained and lost subjects) after 40% attrition.

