4.3 Participants

4.3.1 Randomized Controlled Trial (Aims 1 and 2)

Eligible participants will include vaccinated and unvaccinated LTCWs who self-identify as: 1) being 18 years and older, 2) living in the United States, 3) having worked in a long-term care setting in the past two years, 4) able to verify their LTCW status, 5) not currently pregnant or breastfeeding, and 6) able to read, write, and understand English, and 7) being at least somewhat worried about the COVID-19 vaccines and/or not having received any COVID-19 booster vaccine (see Table 2).

Eligible LTC settings will include nursing homes, skilled nursing facilities, assisted living facilities, home health care, hospice care, and retirement communities. The two-year timeframe will avoid excluding those who are currently unemployed, and will approximately cover the duration of time since the COVID-19 pandemic began. To ensure a high proportion of study participants represent our low confidence target group, we will use two criteria – worry about the vaccines and booster uptake – to screen participants for eligibility. These criteria are based on a preliminary analysis of panel survey data, which found associations between booster intent, worry about the vaccines, and vaccine confidence.

Table 2. Screening questions and eligibility criteria

Question	Eligible Response(s)	Ineligible Response(s)
Can you read, write, and understand English? (adapted from ³⁶)	Yes	No
How old are you?	18-19 years; 20-24 years; 25-29 years; 30-34 years; 35-39 years; 40-44 years; 45-49 years; 50-54 years; 55-59 years; 60-64 years; 65 years or older	Less than 18
Do you live in the United States?	Yes	No
This study is for long-term care workers. We must be sure that everyone who joins is giving us the correct information about who they are. We also need to be sure that everyone has worked in a long-term care setting. It is important to our study results. The information that you provide in this survey will help us confirm your identity and that you are a long-term care worker. We will never contact your employer about your participation in the study.	N/A	N/A
Have you worked in a long-term care setting in the past 2 years? This includes nursing homes, skilled nursing facilities, assisted living facilities, home health care, hospice care, and retirement communities.	Yes	No

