P-values ≥ 0.0001 will be reported to 4 decimal places; p-values less than 0.0001 will be reported as " <0.0001 ". The mean, standard deviation, and any other statistics other than quantiles, will be reported to one decimal place greater than the original data. Quantiles, such as median, minimum, or maximum will use the same number of decimal places as the original data. Estimated parameters, not on the same scale as raw observations (e.g. regression coefficients) will be reported to 3 significant figures.

Adherence to interventions

Analysis of both intention-to-treat (ITT) and as-treated populations will be performed. All participants who are randomized to a trial arm will be included in the ITT analyses. Participants who adhere to major engagement criteria for their primary intervention will be included in the as-treated analyses.

Analysis methodology

Aim 1

To compare the impact of two interventions delivered online: 1) a dialogue-based webinar (webinar) using the existing COVID-19 Option Grid conversation aid and, 2) an interactive and, dynamic, and multi-component social media web application (social media website), compared to enhanced usual practice (link to Centers for Disease Control (CDC) vaccine website), on COVID-19 vaccine confidence (primary outcome), and other secondary outcomes among LTCWs. We hypothesize that each intervention will be superior to enhanced usual practice at increasing vaccine confidence (*Hypothesis 1.1*) and that the dialogue-based webinar intervention will be superior to the social media arm at increasing vaccine confidence (*Hypothesis 1.2*).

Corresponding analyses

Primary outcome

The primary outcome is the binary classifier of vaccine confidence derived from the three-item Vaccine Confidence Index (VCI), evaluated at 3 weeks post-randomization, which will be analyzed by randomization arm. The determined binary predictors of intervention outcomes will be compared using two-proportion z-tests to identify significant differences between each intervention and enhanced usual practice (Arm 1 vs Arm 3 & Arm 2 vs Arm 3 - superiority analyses) and between the intervention arms (Arm 1 vs Arm 2 - two-tailed equivalency analysis).

Secondary outcomes

- *Change from baseline in COVID-19 Vaccine Confidence.* Analysis of change from

baseline will be based on a binary classifier whether the average score increases (1) or does not increase (2) at T1, T2, and T3 versus baseline.

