The primary outcome involves three separate tests, one a two-tailed equivalence test and two one-tailed superiority tests. In order to achieve a family-wise error rate less than 0.050, the Bonferroni method was employed to set a p-value threshold at 0.016 for each of the three primary outcome analyses. For each comparison, mean-value separation will be considered significant based on a 98.4% confidence interval, which translates to +/- 2.45 times the standard

error for the sample mean for the equivalence test and greater than 2.15 times the standard error for the superiority analyses.

Based on the high number of secondary outcome analyses (cross-sectional T1; change from baseline; ITT; as-treated), results data for these outcomes will be viewed in more aggregate form as trending in one direction or not, rather than adopting a specific Bonferroni-corrected p-value threshold.

References

1. B. Rocks, Interval Estimation for the “Net Promoter Score.” *Am. Stat.* 70, 365–372 (2016).
2. R. M. Baron, D. A. Kenny, The moderator–mediator variable distinction in social psychological research: Conceptual, strategic, and statistical considerations. *J. Pers. Soc. Psychol.* 51, 1173–1182 (1986).
3. T.E. Raghunathan, J.M. Lepkowski, J. Van Hoewyk, P. Solenberger, et al. A multivariate technique for multiply imputing missing values using a sequence of regression models. *Surv. Methodol.* 27, 85–96 (2001).

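### The 80% power in section 4.6 is for a two-sided test at 0.05, but Appendix B tests each primary comparison at 0.016; at control rates that reproduce 4.6, power is about 75-77% (superiority) and 64-66% (Arm 1 vs Arm 2)

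*Combined protocol and SAP*

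**What the plan says.** Section 4.6 (Sample Size and Power Calculation) states that 600 per arm "provides 80% power to detect an 8% difference in the rate of scores above this threshold between groups with a two-sided test". The error rate completes the sentence: "with a two-sided test at type I error rate of 0.05". It adds: "The sample size is sufficient to retain 80% power to detect a 10% difference" after 40% attrition, which leaves 360 per arm. It gives no control-arm rate. It says the calculation assumes the analytic approaches set out from section 4.7.2 onward, but 4.7.2 covers consent and identity verification; the statistical analysis is in 4.8 and Appendix B.

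Appendix B (Primary outcome) compares the binary confidence outcome at 3 weeks by two-proportion z-tests: Arm 1 vs Arm 3 and Arm 2 vs Arm 3 for superiority, and a third test "between the intervention arms (Arm 1 vs Arm 2 - two-tailed equivalency analysis". Under Multiple testing, "the Bonferroni method was employed to set a p-value threshold at 0.016 for each of the three primary outcome analyses". The rejection limits are 2.15 standard errors for the one-tailed superiority tests. For Arm 1 vs Arm 2 the plan uses a confidence interval "which translates to +/- 2.45 times the standard" error. No equivalence margin appears anywhere, and no section gives power at these limits.

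**The concern.** The stated 80% belongs to a test the trial will not run. The critical value rises from 1.96 to 2.15 for superiority and to 2.45 for Arm 1 vs Arm 2, while sample size and target difference stay the same, so power must fall. For superiority the move to one-tailed testing offsets part of the loss. For Arm 1 vs Arm 2 nothing does.

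What is at stake is mainly how a null result is read. Webinar against social media is a stated hypothesis (section 3.2), and section 4.8.2 says that finding no distinguishable difference would itself be informative. A reader relying on 4.6 would put the chance of missing a true 8-point difference at 20%, when at the rates that reproduce 4.6 it is about 35%.

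**Working it through.** **Inputs from the documents.** n = 600 per arm with d = 0.08, and n = 600 × 0.60 = 360 per arm with d = 0.10 (section 4.6). Two-proportion z-test (Appendix B, Primary outcome). Critical values z = 1.96 two-sided (4.6), and 2.15 one-tailed and 2.45 two-sided (Appendix B, Multiple testing). The exact two-sided value for 0.016 is 2.41, so 2.45 is slightly stricter than the stated threshold (it corresponds to 0.0143).

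**Assumed.** The control rate p, meaning the lower of the two arms compared, scanned from 5% to 85%. Arm 1 vs Arm 2 is treated as a two-sided difference test, because the plan calls it an equivalence analysis but gives no margin and defines it by ±2.45 standard errors.

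**Formula.** With p₂ = p + d and p̄ = (p + p₂)/2:

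SE₀ = √[2p̄(1 − p̄)/n], SE₁ = √[(p(1 − p) + p₂(1 − p₂))/n], power = Φ[(d − z·SE₀)/SE₁]. The opposite tail is negligible.

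**Worked example, p = 35%, n = 600, d = 0.08.** p̄ = 0.39, SE₀ = 0.02816, SE₁ = 0.02807.
- z = 1.96: (0.08 − 0.05519)/0.02807 = 0.884, power 81.2%
- z = 2.15: (0.08 − 0.06054)/0.02807 = 0.693, power 75.6%
- z = 2.45: (0.08 − 0.06899)/0.02807 = 0.392, power 65.3%

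**Step 1: reproduce section 4.6.** At two-sided 0.05, both statements come out within 2 points of 80% at control rates of about 33-35.5% or 54.5-59%. The table shows the ends of those bands, and 45% for comparison.

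| Control rate | 600/arm, 8 points | 360/arm, 10 points |
|---|---|---|
| 33% | 81.9% | 79.1% |
| 35.5% | 81.0% | 78.1% |
| 45% | 79.2% | 76.6% |
| 54.5% | 80.4% | 78.1% |
| 59% | 81.9% | 79.9% |

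**Step 2: the same rates at the Appendix B limits.**

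| Control rate | z > 2.15, 600/arm, 8 points | z > 2.15, 360/arm, 10 points | abs(z) > 2.45, 600/arm, 8 points | abs(z) > 2.45, 360/arm, 10 points |
|---|---|---|---|---|
| 33% | 76.5% | 73.1% | 66.3% | 62.4% |
| 35.5% | 75.4% | 72.1% | 65.0% | 61.2% |
| 45% | 73.4% | 70.4% | 62.7% | 59.3% |
| 54.5% | 74.7% | 72.1% | 64.2% | 61.2% |
| 59% | 76.5% | 74.2% | 66.3% | 63.6% |

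At the exact 0.016 value of 2.41, Arm 1 vs Arm 2 has 65.7-67.8% power for 8 points over the reproducing rates.

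**Step 3: where 80% is still kept.**

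| Test | 600/arm, 8 points | 360/arm, 10 points |
|---|---|---|
| Superiority (z > 2.15) | below 27.3% or above 64.7% | below 23.1% or above 67.0% |
| Arm 1 vs Arm 2 (abs(z) > 2.45) | below 19.1% or above 72.9% | below 16.2% or above 73.9% |

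**Step 4: sample size for 80% power on 8 points at the reproducing rates.** About 650-680 per arm for superiority and 790-820 per arm at 2.45, against 600.

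**The case against.** The strongest reply is that the control rate is unknown, so the reproducing rates are inferred and not unique. With the same 2-point tolerance, the superiority limit of 2.15 itself yields both statements in 4.6 at a control rate near 25% (81.8% for 8 points, 78.3% for 10 points) or near 65-67%. A low rate is plausible: the outcome requires agreement on all three items (section 4.5.1), and the screening criteria were chosen "To ensure a high proportion of study participants represent our low confidence target group". If keeping 80% means at least 80%, the rates used here do not quite meet the attrition statement even at 0.05 (78.1-79.9%). The superiority loss is also modest, the 64-66% figure depends on 2.45 where 0.016 implies 2.41, and a test called equivalence has been read as a difference test.

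Much of this stands as qualification. The power figures are conditional on the control rate, and superiority may keep 80% if that rate is low. Section 4.6 is correct arithmetic at its own stated error rate, so the fault is that it was not reconciled with Appendix B.

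The alternative rates do not rescue it, however. At 25%, or at 65-67%, the two-sided 0.05 calculation that 4.6 describes gives about 85-86% for 8 points, so the stated 80% would not describe the design, and Arm 1 vs Arm 2 would still have only about 71-74%. Using 2.41 instead of 2.45 adds about 1.5 points.

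**Conclusion.** The concern holds. The power in section 4.6 is not the power of the three primary tests in Appendix B, and the plan does not give the latter. At the rates consistent with both statements in 4.6, the shortfall from 80% is about 3-5 points for superiority and 14-16 points for Arm 1 vs Arm 2 with 600 per arm. After 40% attrition it is about 6-8 and 16-19 points. For Arm 1 vs Arm 2 the 8-point shortfall is present at any control rate from about 20% to 72%; for superiority, from about 28% to 64%.

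These figures rest on an assumed control rate, the usual z-test variance formulas, and Arm 1 vs Arm 2 as a two-sided difference test. Power for a true equivalence test cannot be computed without a margin. This should be fixed, but it does not undermine the design.

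**What to change.** Rewrite the power statement in section 4.6 at the Appendix B limits, state the assumed control rate, and correct the reference to 4.7.2. Differences detectable with 80% power would read:

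| Rates assumed | Test | 600/arm | 360/arm |
|---|---|---|---|
| Two arms centred on 50% | Superiority, z > 2.15 | 8.6 points | 11.1 points |
| Two arms centred on 50% | Arm 1 vs Arm 2, abs(z) > 2.45 | 9.5 points (9.4 at 2.41) | 12.2 points |
| Control 33-35.5% or 54.5-59% | Superiority | 8.3-8.5 points | 10.7-11.0 points |
| Control 33-35.5% or 54.5-59% | Arm 1 vs Arm 2 | 9.1-9.3 points | 11.7-12.1 points |

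Because enrolment is enriched for low confidence, a lower control rate should be shown alongside. State that the Arm 1 vs Arm 2 figure is for a difference test, or give an equivalence margin and the power for it.

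The cost is one or two sentences and less favourable figures. Sample size, tests and thresholds do not change.

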4.7 Trial Procedure

4.7.1 Recruitment and Screening

Prospective participants will be recruited via several online channels. We will co-design engaging recruitment materials with our stakeholder partners, including brief animated videos that describe the study. We will utilize the existing networks of our partner organizations, stakeholders, and consultants, to share recruitment messaging. This will include email listservs and social media platforms (e.g., Facebook groups). We will also utilize paid, targeted social media advertising to share recruitment messaging on various platforms, including Facebook and Instagram, among other platforms. Lastly, we will utilize in-person recruitment which will include sharing recruitment materials during visits to LTC settings, conferences, and other events, and outreach to LTC settings with requests to display study recruitment materials.

Recruitment messaging (i.e., emails, social media ads, posters, table tents, and business cards) will include links to: 1) a study landing page where prospective participants can learn more about the study via brief, plain-language study information in both video and written formats, and, 2) a Qualtrics survey where they can proceed straight to eligibility screening. Screening will involve prospective participants answering a series of questions to self-assess their eligibility (see Table 2). The study landing page will also include a link to the Qualtrics survey.

4.7.2 Consent, Identity Verification, and Baseline Assessment

Those who meet the eligibility criteria will proceed to a study Information Sheet that will provide information about the study objectives, processes, risk, benefits, and data protection and sharing. To improve accessibility and facilitate the uptake of study information, we are also developing an animated video version of the Information Sheet that will contain the same information as the text version. Participants will be able to choose if they want to watch the video or read the text version of the Information Sheet in the online Qualtrics survey platform (or see both). At the end of the Information Sheet, prospective participants will be asked if they have read/watched and understood the information and if they agree to take part in the study. Those who respond 'Yes' to both questions will be considered to have consented to the study and will proceed to the T0 Survey.

Because of the online nature of the trial, incentives provided, and early instances of fraudulent activity⁷², we will implement several strategies to prevent, detect, and respond to fraudulent study enrollment. The strategies we will adopt were informed by a prior review of methods⁷³

and recommendations^{74,75} on this topic. We also engaged our stakeholders in this development process to ensure a range of strategies feasible and acceptable to LTCWs.

First, in the baseline survey, we will add a reCAPTCHA bot detection filter^{73,74,76}, cookie-based settings that prevent multiple submissions from the same web browser^{73,74,77}, and a message discouraging duplicate survey completion^{73,74}. After consent, participants will be asked to provide the name of their current or former workplace and the type of long-term care setting it is. Additionally, in order for us to verify that they have worked in a long-term care setting within the last 2 years, they will be required to choose one of four different verification options:

- 1) *Work ID badge.* Participants will be able to directly upload a photo of their work ID badge, or, arrange a time to speak with us to show their badge over a brief Zoom video call. We will review badge images uploaded/shown to ensure the participant's name, place of work, and LTCW role (if listed) matches the information they have provided in the T0 (baseline) Survey. We will also conduct an online search (using Google Chrome Incognito mode) of workplace names to confirm they are a long-term care setting. Participants' zip codes may also be used to aid in this search, if required.
- 2) *Recent pay stub from the past 2 years.* Participants will be able to directly upload a photo of a prior pay stub from within the past 2 years, or arrange a time to speak with us to show their pay stub over a brief Zoom video call. We will review pay stub images uploaded/shown to ensure the participant's name and place of work matches the information they have provided in the T0 (baseline) Survey. We will also conduct an online search (using Google Chrome Incognito mode) of workplace names to confirm they are a long-term care setting. Participants' zip codes may also be used to aid in this search, if required.
- 3) *Certification or professional license number.* Participants with certain roles (e.g., certified nursing assistants in most states, health care providers) will be able to provide their Certification Number or Professional License Number, alongside the state they are registered in and their associated professional role. We will verify Certification/License Numbers by searching state online registries (e.g., <https://forms.nh.gov/licenseverificationtest/>). Participants' names may also be used to aid in this search, if required. We will also conduct an online search (using Google Chrome Incognito mode) of workplace names reported in the T0 (baseline) Survey to confirm they are a long-term care setting. Participants' zip codes may also be used to aid in this search, if required.
- 4) *Work email account.* Participants who have workplace email accounts will be able to email us directly from their account with their first and last name, the name of their workplace, and the name of the study. We will conduct an online search (using Google Chrome Incognito mode) of workplace names and associated email domains to confirm they match, and that this

place of work matches the information they have provided in the T0 (baseline) Survey and is a long-term care setting. Participants' zip codes may also be used to aid in this search, if required.

We will also employ TransUnion's TLOxp verification service (www.tlo.com), to confirm the identity of participants recruited online⁷⁵. TLOxp aggregates publicly available databases and records to authenticate and verify identity information. We will develop a standardized process for identity verification using participant name, zip code, age range, cell phone number, and email address.

We will inform those who select the option to upload an image of their badge or recent pay stub that we only need to see their name, workplace, and LTCW role (if listed). They will be instructed to cover up any other sensitive information or information they do not wish to share.

Reminder messages (text and email) and phone calls^{73,74} will be utilized to gather further information from participants who fail to provide the requested information in the time frame specified. Participants recruited in person will be presented with the same verification survey questions as other participants, however, the need for follow-up contact to confirm their LTCW status in some situations will be relaxed due to verification not being necessary for this sub-population.

Participants who do not pass a verification check (including those who fail to provide the requested information in the time frame specified) will be sent a message stating that they can no longer remain in the study and will be unenrolled⁷⁴.

Once participants have provided verification information or selected a verification option that requires completion later (e.g., scheduling a video call with a member of the research team), they will proceed to the remainder of the T0 Survey. The T0 Survey will include capturing participant contact information and an assessment of outcomes indicated in Table 3 and participant characteristics.

4.7.3 Allocation of Interventions

We will use the randomizer function built into the online Qualtrics survey platform to allocate participants to a trial arm and associated intervention. At the very end of the T0 Survey, the Qualtrics survey platform will automatically generate participants' trial arm and they will be presented with basic information pertaining to their assigned intervention at that time. A 1:1:1 allocation ratio will be used. After submitting their survey, those randomized to Arm 1 (Dialogue-Based Webinar) will be automatically redirected to a separate Qualtrics survey where they can sign up for one of several pre-scheduled webinar sessions. Those randomized to Arm 2 (Social Media Website) will be automatically redirected to the Social Media Website. In order

to access website content, they will first be required to create a username and password for the site. Those randomized to Arm 3 (Enhanced Usual Practice) will be automatically redirected to a specific page(s) on the CDC website (<https://www.cdc.gov/coronavirus/2019-ncov/vaccines/index.html>).

